**REDACTED FOR PUBLIC RELEASE OF THE SAP**

#### Table: Modification of statin effect on changes in NCP and total plaque volume

- By baseline value, sex, age, screening CD4, and duration of suppressive ART

*Depending on their baseline prevalence, modification of the statin effect by use of cardiovascular medications may also be explored.*

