Failure to start statin : Included per randomized treatment (treatment policy) Change in statin strategy : Included per randomized treatment (treatment policy) Includes discontinuation or change of statin Evidence of critical stenosis at treatment start : Included per randomized strategy (treatment strategy) Interval stent placement or bypass *: Included per randomized strategy (treatment policy strategy) Death prior to Year 2 scan : Treated as missing data (hypothetical policy)	Missing data due to missed visits or unreadable scans will be assumed missing completely at random and ignored i.e., the primary analysis will be a complete case analysis including participants with pair baseline and year 2 scans. Sensitivity analyses will include multiple imputation for missing data.
Population-level summary measure	Analysis approach
Mean change NCP volume over 2 years	Linear regression (normal errors assumption). In the event of extreme violation of normality, outcomes will be log transformed (giving a percentage change interpretation of the treatment effect). Modeling will adjust for CD4 and sex (stratification factors), and for baseline NCP volume.

\* Stented or bypassed coronary artery segments are not considered on the entry and year 2 scan as part of the read protocol for plaque volume.

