## 7 Analysis Plan

### 7.1 General analysis Considerations

Outcome distributions will be described with median, Q1, Q3, P10, P90, minimum, and maximum and shown graphically. All primary treatment group comparisons will be performed ITT using a 5% type error. For continuous outcomes, inference will be based on differences in means adjusted for baseline and presented with two-sided, 95% confidence intervals.

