#### Table: Primary and secondary plaque outcomes

Among participants with plaque at entry, descriptive statistics for the change and percentage change in NCP volume over 2 years will be provided by treatment group with group comparisons made with linear regression with adjustment for baseline plaque volume and stratified by sex and CD4.

Among those without NCP at entry, the prevalence of incident NCP over 2 years will be compared with stratified chi-squared test.

To assess the mechanistic study population as a whole, the probability of NCP and total plaque progression over two years (see Section 3.2.2) will be compared by treatment group using a stratified chi-squared test.

The statin effect on high risk plaque features (any), including low attenuation and positive remodeling, will be assessed by comparing differences in the 2-year prevalence of high risk plaque morphology features between treatment groups using chi-squared (or Fisher's exact) tests as appropriate; these analyses will be performed overall and by subgroups defined by the presence of NCP at study entry.

*Sample table from Testosterone study, JAMA 2017*

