### 7.3 Statin effects on markers of immune function and markers of glucose homeostasis

Outcome measures: See Sections 3.4 and 3.5

Statin effects on the distributions of blood biomarkers belonging to distinct pathways will be assessed via treatment group comparisons of these respective markers via linear regression with adjustment for baseline and stratified by sex and CD4.

We will examine modification of statin effect on these markers by baseline value, sex, age, screening CD4, duration of suppressive ART, and presence of NCP at study entry.

Figure: Distributions of lipid fractions by treatment group over time

- Violin plots

Figure: Mean and 95% CI lipid fractions by treatment group over time

Table: Median, Q1, Q3 and Mean and 95% CI lipid fractions by treatment group over time

*Sample table from Atorvastatin trial Lancet 2015*

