## Appendix I Sample Size Considerations

[Copied Verbatim from the REPRIEVE A5333S Protocol, Version 5.0, Section 9.2.]

The target sample size for the Mechanistic Substudy of REPRIEVE (A5333s) is 800 participants that will be approximately equally distributed between the study arms.

This sample size was determined to have high power to detect clinically relevant differences between the two study groups both with respect to plaque progression (among those with plaque at study entry) and rates of incident plaque (among those plaque-free at entry). Specifically, the total sample size of 800 subjects will provide 90% power to detect a 6% difference between the study groups in the percent change in NCP volume over 2 years among those with plaque at entry and 90% power to detect 13 percentage point difference in the probability of plaque development over 2 years. These effect sizes translate to a combined estimated 14 percentage point difference in the probability of NCP progression over two years and are based on the following assumptions:

50% of study participants will have evidence of NCP at study entry [Lo 2010]

A SD of 20% for the percent change over 2 years among participants with evidence of plaque at entry

An annual rate of incident plaque development of 12% among participants without plaque at entry

15% of participants entering the substudy will not be evaluable for study entry or 2 year NCP volume.

Together, the effects of statins acting in these two groups (those with and without evidence of NCP at study entry) will provide for a 7% lower prevalence of NCP after 2-years of statin treatment. Expectations for NCP prevalence and progression both as a whole and according to whether NCP was present at study entry are illustrated in the table below. These estimates are based on a simulation that further assumed the following:

Average volume NCP 250mm^3 (SD=200) among participants with NCP at entry.

Average volume NCP 40mm^3 (SD=20) at 2 years among participants without NCP at entry without statin treatment.

Average volume NCP 20mm^3 (SD=20) at 2 years among participants without NCP at entry with statin treatment.

NCP distributions were also assumed to follow a gamma distribution with size and shape parameters determine to provide the desire mean and standard deviations.

Table 9.2-1: Cells constituting the primary targeted group comparisons are shown in bold.

		At study entry			At two 2 years						

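### SAP 7.2 names no model for modification of the statin effect by entry plaque volume; extending the SAP's own linear regression on mm³ change would give roughly 35–37% false positives under the Appendix I planning model

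*SAP*

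**What the plan says.** The item in SAP 7.2 is a heading, "Table: Modification of statin effect on changes in NCP and total plaque volume", followed by one line of modifiers: "By baseline value, sex, age, screening CD4, and duration of suppressive ART". It does not name a model, an interaction term, a test, a standard error, the scale of change, or whether entry volume is continuous or grouped.

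The surrounding text points in one direction. The primary estimand table (SAP 2.1) makes absolute change in NCP volume the continuous outcome measure and gives the analysis approach as "Linear regression (normal errors assumption"). SAP 7.2 has "group comparisons made with linear regression with adjustment for baseline plaque volume and stratified by sex and CD4". SAP 7.1 bases inference for continuous outcomes on baseline-adjusted mean differences. SAP 3.2.1 labels percentage change as supportive. Robust variance is not mentioned anywhere.

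There is one fallback, in SAP 2.1: "In the event of extreme violation of normality, outcomes will be log transformed (giving a percentage change interpretation of the treatment effect").

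On spread, Appendix I assumes "A SD of 20% for the percent change over 2 years among participants with evidence of plaque at entry", together with gamma-distributed entry volumes of mean 250 and SD 200 mm³. SAP 7.3 plans the same kind of analysis for the blood markers: "We will examine modification of statin effect on these markers by baseline value, sex, age, screening CD4".

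**The concern.** If the SD of percent change is the same for everyone, the SD of change in mm³ rises in proportion to entry volume. Model-based standard errors from ordinary regression assume one common residual variance. For the main arm effect in a randomised comparison with equal arms, this does little harm. For the arm × entry-volume slope it matters a great deal. The slope is determined mainly by participants with large volumes, and they are the ones with the largest errors, so the reported standard error is much too small.

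At stake is a prominent secondary message, namely that pitavastatin acts differently in people with more plaque. The analysis could report this when there is no difference.

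**Working it through.** **Inputs (SAP Appendix I).** 800 participants in equal arms; 15% not evaluable; 50% with NCP at entry. Evaluable: 800 × 0.85 = 680, of whom 340 have NCP at entry (170 per arm). Entry volume V is gamma with mean 250 and SD 200, so shape = (250/200)² = 1.5625 and scale = 200²/250 = 160. SD of percent change is 20%. The test is two-sided at 5%.

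**Reproducing the plan's figures.** The SAP states no error rate for modification, so the figures to reproduce are the SDs of absolute change in its Table 9.2-1. With percent change of mean m and SD 0.20, independent of V:

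SD(change) = √[0.04 × E(V²) + m² × Var(V)], with E(V²) = 250² + 200² = 102,500 and Var(V) = 40,000.

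- Control, m = 0.12: √(4,100 + 576) = 68.4; the table has 68.
- Statin, m = 0.05: √(4,100 + 100) = 64.8; the table has 64.

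The planning table therefore does have mm³ scatter proportional to entry volume. The 170 per arm is also consistent with it: the table's 12% versus 5% with SD 20% gives 89.7% power. (The 6-point difference in the text gives 79.0%; that is a separate matter.)

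**Large-sample size of the interaction test.** Residual variance at volume V is 0.04V². The ratio of the true to the model-based variance of the interaction slope is

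E[(V − 250)²V²] / [Var(V) × E(V²)].

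The gamma moments are E(V³) = 58,425,000 and E(V⁴) = 42,650,250,000. The numerator is 42,650,250,000 − 500 × 58,425,000 + 62,500 × 102,500 = 19,844,000,000. The denominator is 40,000 × 102,500 = 4,100,000,000. The ratio is 4.84, and √4.84 = 2.2.

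Type I error = 2[1 − Φ(1.96/2.2)] = 37%.

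**Simulation under the null.** Both arms follow the same law of change (4,000 to 10,000 trials per setting for NCP at entry, 4,000 to 5,000 for the whole population). The regression contains sex, CD4, arm, V and arm × V. Normal, lognormal and skewed percent changes gave similar results.

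| Test of arm × entry volume | NCP at entry (340) | Whole population (680) |
|---|---|---|
| mm³ change, continuous V, model-based SE | 34–37% | 45–48% |
| Same, HC3 SE | 5.0–5.6% | 5.3–6.1% |
| Percentage change as outcome | 4.5–5.1% | not run |
| Log ratio or log volume | 4.2–5.4% | 3.9% (log of volume + 1) |
| mm³ change, V split at the median (whole population: NCP present or absent) | 4.1–5.2% | 4.3–5.3% |
| mm³ change, tertile trend | 8% | not run |
| Main arm effect, mm³ change | 4.3–5.3% | 4.1–5.5% |

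**Sensitivity to strict proportionality.** Suppose a fraction f of the average residual variance is constant (an assumption; the documents give no such split). The ratio becomes 4.84(1 − f) + f:

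- f = 0.25: ratio 3.88, type I error 32%.
- f = 0.50: ratio 2.92, type I error 25%.
- f = 0.75: ratio 1.96, type I error 16%.

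The inflation shrinks if scatter is only partly proportional, but it stays well above 5% across this range.

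**The case against.** **The method is inferred.** SAP 7.2 does not say that modification is tested by ordinary regression. The statement "All primary treatment group comparisons will be performed ITT using a 5% type error" covers primary comparisons, and this table is not one. The 35–37% needs four choices together: mm³ change, continuous entry volume, model-based standard errors and no log transformation. Changing any one brings the rate to about 5%, or 8% for a tertile trend. Percentage change is a listed outcome and would be safe. All of this stands, so the finding is conditional. It remains more than a missing detail, because the only regression that the SAP states, applied to its main continuous outcome, is the version that fails.

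**The log fallback may apply.** Under the planning model, unequal spread produces heavy-tailed residuals. In simulation a Shapiro test gave p < 0.001 in essentially every trial, with median excess kurtosis of about 6 (NCP at entry) or 12 (whole population). The fallback could therefore be invoked, and among those with NCP at entry it restores about 5%. This partly stands. However, the trigger has no threshold and does not refer to unequal spread. Changes can be negative (Table 9.2-1 has 5th percentiles of −38 and −66 mm³) and so cannot be logged as written. Zero volumes need an offset that the SAP does not give.

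**The whole-population figure needs a broader reading.** SAP 7.2 limits its regression to participants with plaque at entry and assesses the whole population by progression. The 46% applies only if the analysis set in the SAP 2.1 estimand is carried into the modification table.

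**Stronger readings that the documents do not support.** A reader might infer that the planned effect also yields false positives, since ordinary regression then rejects in 54% (NCP at entry) and 70% (whole population) of trials. It does not: under 12% versus 5% growth the mm³ effect truly grows with entry volume, so modification on that scale is real. A reader might also attach an error rate to the blood markers in SAP 7.3. The documents give no marker distributions, so none can be quoted.

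**Conclusion.** The concern holds in conditional form. If the modification analysis extends the SAP's linear model to a continuous arm × entry-volume term on mm³ change with model-based standard errors, its false-positive rate under the Appendix I planning model is about 35–37% among participants with NCP at entry, and about 46% if everyone is included. Null here means the same distribution of change in both arms. The result rests on a constant 20% SD of percent change, gamma entry volumes of mean 250 and SD 200 mm³, and the planned evaluable numbers. The primary arm comparison is sound. Severity is low to moderate: a non-primary analysis is affected, but the inflation is large and the correction costs little.

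**What to change.** In SAP 7.2:

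- State the model for effect modification and use HC3 heteroscedasticity-robust standard errors for all modification terms.
- Test modification by entry volume on a relative scale (log of year-2 over entry volume, or percentage change) in participants with NCP at entry, and state how entry volume is coded and how any zero year-2 volume is handled.
- Label any modification shown in mm³ as absolute-scale only, because a constant relative effect will appear there as modification.

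In SAP 7.3, use HC3 for the baseline-value modification terms as a precaution against skewed markers.

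The cost is a few sentences and one software option. The downside is slightly lower power for the interaction if the errors do have constant variance.

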### 7.3 Statin effects on markers of immune function and markers of glucose homeostasis

Outcome measures: See Sections 3.4 and 3.5

Statin effects on the distributions of blood biomarkers belonging to distinct pathways will be assessed via treatment group comparisons of these respective markers via linear regression with adjustment for baseline and stratified by sex and CD4.

We will examine modification of statin effect on these markers by baseline value, sex, age, screening CD4, duration of suppressive ART, and presence of NCP at study entry.

Figure: Distributions of lipid fractions by treatment group over time

- Violin plots

Figure: Mean and 95% CI lipid fractions by treatment group over time

Table: Median, Q1, Q3 and Mean and 95% CI lipid fractions by treatment group over time

*Sample table from Atorvastatin trial Lancet 2015*

**REDACTED FOR PUBLIC RELEASE OF THE SAP**

### 7.4 Statin effects on lipids

Outcome measures: See Section 3.6.2

Figure: Distributions of lipid fractions by treatment group over time

- Violin plots

Figure: Mean and 95% CI lipid fractions by treatment group over time

Table: Mean and 95% CI lipid fractions by treatment group over time

### 7.5 LDL and blood biomarkers as mediators for plaque progression

In the event that both statin effects on NCP progression and biomarker changes are apparent, the association between changes in LDL and these biomarkers and NCP progression will be examined using graphical techniques and normal errors and logistic regression (for the subpopulations with and without NCP at entry respectively. A mediating effect of these biological factors will be evaluated by examination of changes in the estimated statin effect on NCP upon adjustment for these biological factors.

Since the hypothesized mechanism is that sustained high levels of immune activation and inflammation precede and contribute to progression of NCP volume and high risk plaque features, these analyses will relate short term changes in these biomarkers (over 4 months) to longer term changes in NCP volume and morphology after two years.

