LDL and blood biomarkers as mediators for plaque progression: In the event that both statin effects on NCP progression and biomarker changes are apparent, the association between changes in LDL and these biomarkers and NCP progression will be examined using graphical techniques and normal errors and logistic regression (for the subpopulations with and without NCP at entry respectively. A mediating effect of these biological factors will be evaluated by examination of changes in the estimated statin effect on NCP upon adjustment for these biological factors. Those biomarkers with the strongest mediating effect on plaque progression will be measured in the entire REPRIEVE (A5332) cohort to determine their association with MACE.

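### SAP 7.5 reads mediation of incident NCP from the change in a logistic statin effect, which mixes mediation with an opposite scale shift that differs by marker and can reorder the mediators

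*SAP*

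**What the plan says.** SAP 7.5 sets up two models: the associations are to be "examined using graphical techniques and normal errors and logistic regression (for the subpopulations with and without NCP at entry respectively". Participants with NCP at entry get a linear model and those without get a logistic model for incident plaque. In both, mediation is to be "evaluated by examination of changes in the estimated statin effect on NCP upon adjustment for these biological factors". Protocol Appendix II, 9.5.2 has the same rule: "A mediating effect of these biological factors will be evaluated by examination of changes in the estimated statin effect on NCP".

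The analysis runs only "In the event that both statin effects on NCP progression and biomarker changes are apparent". It is meant to "relate short term changes in these biomarkers (over 4 months) to longer term changes in NCP volume and morphology after two years".

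Neither document names the effect scale for the before-and-after comparison, a decomposition into direct and indirect effects, or an interval for the change. Protocol 9.5.2 adds a use for the result that SAP 7.5 does not repeat: the markers with the strongest mediating effect on plaque progression will be measured in the whole REPRIEVE cohort. SAP 2.2 lists the relative contributions of immune activation and traditional factors, including LDL, as a secondary objective.

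**The concern.** In a linear model with a randomised treatment, adding a marker the statin does not move leaves the expected treatment coefficient unchanged, so a change on adjustment can be read as mediation. A logistic coefficient does not behave this way. Conditioning on a predictor of plaque makes the statin log odds ratio larger in absolute size even if the statin leaves that predictor alone. For a real mediator, this scale shift offsets part of the fall that mediation produces.

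The size of the offset depends on how well the marker predicts plaque, so it is not a common factor that cancels when markers are compared. At stake is the order of the mediators, and under Protocol 9.5.2 that order decides which assays are run on the full cohort.

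**Working it through.** **The plan's own figure.** SAP Appendix I gives 800 participants, 15% not evaluable, 50% free of NCP at entry and equal arms: 800 × 0.85 × 0.50 / 2 = 170 per arm in the logistic subset. With 21% versus 8% at two-sided 5%, power is 92.9%. Using 12% a year compounded (22.6%) and 13 points less (9.6%), it is 90.7%. The stated 90% is reproduced.

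**Design odds ratio.** logit(0.08) − logit(0.21) = −1.117, an odds ratio of 0.327. Its SE at 170 per arm is √(1/35.7 + 1/134.3 + 1/13.6 + 1/156.4) = 0.34, with 35.7 + 13.6 = 49.3 expected events.

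**Model for the check.** The marker is Normal with SD 1 in both arms and is lowered by a SD on statin. The outcome is logistic in treatment (coefficient c) and marker (coefficient b = ln of the odds ratio per SD), with no interaction. The marginal risks are held at 21% and 8% and solved by quadrature. The documents give neither a nor b, so both are assumed over a range.

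- Share by the SAP rule: (1.117 − |c|) / 1.117.
- Share free of the scale shift, on the logit scale: ab / (ab + |c|). The natural indirect effect on the logit scale agrees within about 1 point.

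**No mediation (a = 0).** The adjusted log odds ratio is −1.151, −1.182 and −1.252 at odds ratios of 1.65, 2.0 and 2.7 per SD. The last, for example, gives (1.117 − 1.252) / 1.117 = −12%. The three apparent shares are −3%, −6% and −12%.

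**With mediation.** In this model |c| = T − ab, where T is the corresponding a = 0 value (1.139 at an odds ratio of 1.5, then 1.151, 1.182 and 1.252). The scale shift T − 1.117 therefore depends on b and not on a.

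| Statin shift a (SD) | OR per SD | SAP rule | Free of scale shift | Understatement (points) |
|---|---|---|---|---|
| 1.0 | 1.5 | 34.3% | 35.6% | 1.3 |
| 1.0 | 2.0 | 56.2% | 58.6% | 2.4 |
| 0.3 | 2.0 | 12.8% | 17.6% | 4.8 |
| 0.3 | 2.7 | 14.6% | 23.8% | 9.2 |
| 0.2 | 2.0 | 6.6% | 11.7% | 5.1 |
| 0.2 | 2.7 | 5.7% | 15.9% | 10.1 |

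(Understatement is taken before rounding.)

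**Ranking.**

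- Marker A: a = 0.3, OR 1.65 per SD, ab = 0.150. SAP rule: (1.117 − 1.001) / 1.117 = 10.4%. Free of shift: 0.150 / 1.151 = 13%.
- Marker B: a = 0.2, OR 2.7 per SD, ab = 0.199. SAP rule: (1.117 − 1.053) / 1.117 = 5.7%. Free of shift: 0.199 / 1.252 = 16%.

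The SAP rule puts A first. The logit product puts B first, and so do both risk-difference decompositions: about 11% against 9% for the total indirect effect, and about 21% against 18% for the pure indirect effect.

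**When the expected share is negative.** This needs an odds ratio per SD above 2.1 at a = 0.10, 3.0 at a = 0.15 and 4.5 at a = 0.20.

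**Sampling.** In 3,000 simulated samples of 340, the SAP rule gave a negative share in 0.4% (a = 1, OR 1.5), 3.6% (a = 0.3, OR 2) and 19% (a = 0.2, OR 2).

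**The case against.** The case against is substantial, and much of it stands.

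- **A reader might infer that adding any predictive marker drives the odds ratio away from 1, so that mediation tends to look negative.** That is true only for predictors the statin does not move. For a real mediator the net move is normally toward 1: at a 1 SD shift the odds ratio goes from 0.327 to 0.480 (OR 1.5 per SD) or 0.613 (OR 2.0). The SAP's condition that biomarker changes be apparent is meant to keep unmoved markers out.
- **A reader might infer that LDL mediation is materially understated.** For an LDL-like marker the gap is about 2 points, small against the sampling error.
- **A reader might compare a true share on the risk scale with the change on the logit scale.** That mixes scales. Going from 21% to 17.75% removes 25% of the risk difference but only 18.7% of the log odds ratio, with no adjustment involved. The direction also depends on the decomposition: at a = 1 and OR 2.0 the total indirect effect on risk is 49%, so the SAP rule's 56% would overstate it.
- **The analysis is exploratory and names no scale.** Standardised reporting is already compatible with the text, and the SAP does not say that the two subpopulations will be compared or pooled.

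What this leaves untouched is the ranking. What counts as an apparent change is not defined. A shift reaches p<0.05 at 1.96√(2/340) = 0.15 SD in the whole evaluable substudy, so markers moved by 0.2 to 0.3 SD can enter. In the plaque-free subset alone the threshold is 1.96√(2/170) = 0.21 SD, which would be borderline for marker B.

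**Conclusion.** The concern holds in a limited form. On its natural reading, the rule in SAP 7.5 and Protocol 9.5.2 carries a scale shift of about −3% to −12% of the log odds ratio for markers with odds ratios of 1.65 to 2.7 per SD. Logit-scale understatement is about 2 points or less for a strongly moved LDL-like marker, and about 5 to 10 points for markers moved by 0.2 to 0.3 SD with odds ratios of 2.0 to 2.7. An expected negative share arises only for markers the statin barely moves. The practical consequence is a possible reversal in the order of mediators, where Protocol 9.5.2 attaches a decision to that order.

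This rests on the planned 21% and 8%, a Normal marker with equal spread in both arms, no treatment-by-marker interaction, one marker at a time, and assumed marker effects. With about 49 events, sampling error in one trial can exceed the shift: at a = 0.3 and OR 2.0 the change has an SD of 0.083, against a shift of 1.182 − 1.117 = 0.065. The shift is systematic, however, and can be avoided.

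**What to change.** Keep the logistic model for incident NCP and change what is reported from it:

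1. Compute the total, direct and indirect effects of statin as standardised risk differences by g-computation from the outcome and marker models, with the adjustment covariates named.
2. State in advance whether the indirect effect is the pure or the total one. The two differ materially (68% against 49% at a = 1 and OR 2.0), so standardising alone does not settle the answer.
3. Rank mediators on that scale, including for the choice of full-cohort assays in Protocol 9.5.2.
4. Give bootstrap intervals for each indirect effect.

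The cost is SAP wording and slightly more analysis work on data already collected.
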